10.1.1. Incidence of Treatment-Emergent Adverse Events

The TEAEs during Treatment Period will be summarized by treatment group, SOC, PT, relationship and intensity, displaying the number and percentage of patients with at least one TEAE using only the worst intensity recorded at each level of summarization. The

total number of events and number of patients with at least one TEAE over all SOC's will also be displayed. In addition, TEAEs regardless of relationship will be summarized.

10.1.2. Deaths

All patients who have a SAE with serious criteria of "Death" will be presented in a listing and the following variables will be included; Safety Set flag, ITTI Set flag, date of the study drug administration, date of last visit, date of death, time to death from the study drug administration, TEAE flag, SOC/PT, cause of death, whether an autopsy was performed (yes, no), whether a death certificate was completed (yes, no), relationship to the study drug, period flag. Time (days) to death from the study drug administration will be calculated as (date of death – date of the study drug administration + 1).

10.1.3. Serious Adverse Events

A SAE is defined as any event that results in death, is life threatening, requires inpatient hospitalization or prolongation of existing hospitalization, results in persistent or significant disability/incapacity, or is a congenital anomaly/birth defect. Important medical events that may not result in death, be life threatening, or require hospitalization may be considered an SAE when, based upon appropriate medical judgment, they may jeopardize the patient and may require medical or surgical intervention to prevent one of the outcomes listed in this definition.

Treatment-Emergent Serious Adverse Events (TESAEs) during Treatment Period will be summarized by treatment group, SOC, PT, relationship, intensity or serious criteria, displaying the number and percentage of patients with at least one TESAE using only the worst intensity recorded at each level of summarization. The total number of events and number of patients with at least one TESAE over all SOC's will also be displayed.

Serious criteria and SAE description will be presented in an additional information listing.

10.1.4. Treatment-Emergent Adverse Events Leading to Study Drug Discontinuation

All patients who have a TEAE with an action taken with study drug of "Drug Withdrawn" during Treatment Period will be summarized by treatment group and by SOC, PT, relationship and intensity, displaying the number and percentage of patients with at least one TEAE leading to study drug discontinuation, using only the most severe TEAE recorded at each level of summarization. The total number of events and number of patients with at least one TEAE leading to study drug discontinuation over all SOC's will also be displayed.

10.1.5. Treatment-Emergent Adverse Events of Special Interest

The AEs checked as infusion related reactions (IRR) including hypersensitivity and anaphylactic reactions on the "Adverse Event" page of eCRF will be classified as treatment-emergent adverse events of special interest (TEAESI). All TEAESI during Treatment Period will be summarized by treatment group, SOC, PT, relationship and

intensity, displaying number and percentage of patients with at least one TEAESI using only the worst intensity recorded at each level of summarization. The total number of events and number of patients with at least one TEAESI over all SOCs will also be displayed. In addition, a table for signs and symptoms regarding IRR will be provided separately by SOC, PT and intensity. Signs and symptoms of IRR including hypersensitivity and anaphylactic reactions will be presented in an additional information listing.

10.2. Clinical Laboratory Evaluations

Blood and urine samples for clinical laboratory assessments (clinical chemistry, hematology and urinalysis) will be collected at each scheduled visit specified in [Appendix 1](#).

The following clinical laboratory assessment will be performed:

Clinical chemistry: Total protein, serum bilirubin (total, direct), ALT, AST, alkaline phosphatase, γ -glutamyl transferase, blood urea nitrogen, creatinine, creatine kinase, creatine kinase-myocardial band isoenzyme, troponin (I or T, [only one applicable]), albumin, sodium, potassium, calcium, chloride, inorganic phosphorus, glucose, lactate dehydrogenase, total cholesterol, triglyceride, high-density lipoprotein cholesterol, and CRP

Hematology: Red blood cells, erythrocyte sedimentation rate (local), total white blood cell count, absolute neutrophil count, eosinophil count, lymphocyte count, platelet count, hemoglobin, mean corpuscular volume, mean corpuscular hemoglobin, mean corpuscular hemoglobin concentration, and hematocrit

Urinalysis: Bilirubin, blood, glucose, ketones, leukocytes, nitrite, pH, protein, specific gravity, urobilinogen, and microscopic examination of white blood cell count, red blood cell count, and bacteria

All summaries will be based on the System International (SI) units based on CTCAE v5.0.

All parameters analyzed at the central laboratory, not limited as specified in the protocol, and ESR analyzed at the local laboratory will be included in summary tables. All parameter results regardless of central or local laboratory will be presented in listings.

Actual value and change from baseline for clinical chemistry and hematology results will be summarized by treatment group at each time point using descriptive statistics. For the

purpose of summarization, any numeric values recorded below the lower limit or above the upper limit of quantification will be set to the respective limit for all related summaries. In listings, original results containing inequality signs will be displayed. Shift tables from baseline visit to each scheduled post-baseline visit will be generated for urinalysis results using “Normal” or “Abnormal” classification as appropriate by treatment group.

Some numeric parameters will be labeled with a CTCAE term, and grading will be applied to post-baseline values for numeric parameters where possible according to CTCAE v 5.0. Grades that require clinical input only will not be assigned to these parameters. Grades which are part numeric and part clinical input will be assigned based on the numeric portion only. If different grades share the same criteria due to exclusion of clinical input, lower grade will be used. The CTCAE terms and ranges for applicable parameters are listed in [Appendix 3](#). The CTCAE grades for this analysis will be Grade 1 (Mild), Grade 2 (Moderate), Grade 3 (Severe) and Grade 4 (Life-threatening). The CTCAE Grade 5 (Death) will not be applied in this analysis since death cannot be determined from a numeric laboratory result. If the post-baseline result for a patient does not satisfy any CTCAE grade, it will be classified as “No Grade”.

The number and percentage of patients with a result for each grade will be summarized by laboratory category, treatment group, CTCAE term and visit. Additional tables will be generated using the most severe grade after study drug administration. The most severe grade will be selected including unscheduled visits.

Clinical chemistry, hematology and urinalysis data will be presented in separate listings along with high and low flags, if applicable, to show if a value was outside the normal range and CTCAE results for applicable parameters.

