7.8.4.3 Clinical Laboratory Test

Actual values and changes from baseline for numeric clinical laboratory test (clinical chemistry, hematology and urinalysis) results will be summarized by each treatment group at each scheduled visit using descriptive statistics. Shift tables will be generated for categorical clinical laboratory test results.

Individual clinical laboratory and pregnancy tests results will be presented in data listings.

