Appendix 3: Table of CTCAE v5.0 Terms and Grades

CTCAE Term	Laboratory Parameter	Level	Grade 1	Grade 2	Grade 3	Grade 4
Blood bilirubin increased	Serum Bilirubin (Total)	High	>ULN - 1.5 x ULN if baseline was normal; > 1.0 - 1.5 x baseline if baseline was abnormal	>1.5 - 3.0 x ULN if baseline was normal; >1.5 - 3.0 x baseline if baseline was abnormal	>3.0 - 10.0 x ULN if baseline was normal; >3.0 - 10.0 x baseline if baseline was abnormal	>10.0 x ULN if baseline was normal; >10.0 x baseline if baseline was abnormal
Alanine aminotransferase increased	Alanine aminotransferase (ALT)	High	>ULN - 3.0 x ULN if baseline was normal; 1.5 - 3.0 x baseline if baseline was abnormal	>3.0 - 5.0 x ULN if baseline was normal; >3.0 - 5.0 x baseline if baseline was abnormal	>5.0 - 20.0 x ULN if baseline was normal; >5.0 - 20.0 x baseline if baseline was abnormal	>20.0 x ULN if baseline was normal; >20.0 x baseline if baseline was abnormal
Aspartate aminotransferase increased	Aspartate aminotransferase (AST)	High	>ULN - 3.0 x ULN if baseline was normal; 1.5 - 3.0 x baseline if baseline was abnormal	>3.0 - 5.0 x ULN if baseline was normal; >3.0 - 5.0 x baseline if baseline was abnormal	>5.0 - 20.0 x ULN if baseline was normal; >5.0 - 20.0 x baseline if baseline was abnormal	>20.0 x ULN if baseline was normal; >20.0 x baseline if baseline was abnormal
Alkaline phosphatase increased	Alkaline Phosphatase	High	>ULN - 2.5 x ULN if baseline was normal; 2.0 - 2.5 x baseline if baseline was abnormal	>2.5 - 5.0 x ULN if baseline was normal; >2.5 - 5.0 x baseline if baseline was abnormal	>5.0 - 20.0 x ULN if baseline was normal; >5.0 - 20.0 x baseline if baseline was abnormal	>20.0 x ULN if baseline was normal; >20.0 x baseline if baseline was abnormal
GGT increased	γ -Glutamyl Transferase	High	>ULN - 2.5 x ULN if baseline was normal; 2.0 - 2.5 x baseline if baseline was abnormal	>2.5 - 5.0 x ULN if baseline was normal; >2.5 - 5.0 x baseline if baseline was abnormal	>5.0 - 20.0 x ULN if baseline was normal; >5.0 - 20.0 x baseline if baseline was abnormal	>20.0 x ULN if baseline was normal; >20.0 x baseline if baseline was abnormal
Creatinine increased	Creatinine	High	>ULN - 1.5 x ULN	>1.5 - 3.0 x baseline; >1.5 - 3.0 x ULN	>3.0 x baseline; >3.0 - 6.0 x ULN	>6.0 x ULN
CPK increased	Creatine Kinase	High	>ULN - 2.5 x ULN	>2.5 x ULN - 5 x ULN	>5 x ULN - 10 x ULN	>10 x ULN
Hypoalbuminemia	Albumin	Low	<LLN - 3 g/dL; <LLN - 30 g/L	<3 - 2 g/dL; <30 - 20 g/L	<2 g/dL; <20 g/L	

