Hypernatremia	Sodium	High	>ULN - 150 mmol/L	>150 - 155 mmol/L;	>155 - 160 mmol/L;	>160 mmol/L;
Hyponatremia	Sodium	Low	<LLN - 130 mmol/L	125-129 mmol/L	120-124 mmol/L	<120 mmol/L;
Hyperkalemia	Potassium	High	>ULN - 5.5 mmol/L	>5.5 - 6.0 mmol/L;	>6.0 - 7.0 mmol/L;	>7.0 mmol/L;
Hypokalemia	Potassium	Low	<LLN - 3.0 mmol/L	<LLN - 3.0 mmol/L; #	<3.0 - 2.5 mmol/L;	<2.5 mmol/L;

Hypercalcemia	Calcium	High	Corrected serum calcium of >ULN - 11.5 mg/dL; >ULN - 2.9 mmol/L; @	Corrected serum calcium of >11.5 - 12.5 mg/dL; >2.9 - 3.1 mmol/L; @	Corrected serum calcium of >12.5 - 13.5 mg/dL; >3.1 - 3.4 mmol/L; @	Corrected serum calcium of >13.5 mg/dL; >3.4 mmol/L; @
Hypocalcemia	Calcium	Low	Corrected serum calcium of <LLN - 8.0 mg/dL; <LLN - 2.0 mmol/L; @	Corrected serum calcium of <8.0 - 7.0 mg/dL; <2.0 - 1.75 mmol/L; @	Corrected serum calcium of <7.0 - 6.0 mg/dL; <1.75 - 1.5 mmol/L; @	Corrected serum calcium of <6.0 mg/dL; <1.5 mmol/L; @
Hypoglycemia	Glucose	Low	<LLN - 55 mg/dL; <LLN - 3.0 mmol/L	<55 - 40 mg/dL; <3.0 - 2.2 mmol/L	<40 - 30 mg/dL; <2.2 - 1.7 mmol/L	<30 mg/dL; <1.7 mmol/L;
Cholesterol high	Total Cholesterol	High	>ULN - 300 mg/dL; >ULN - 7.75 mmol/L	>300 - 400 mg/dL; >7.75 - 10.34 mmol/L	>400 - 500 mg/dL; >10.34 - 12.92 mmol/L	>500 mg/dL; >12.92 mmol/L
Hypertriglyceridemia	Triglyceride	High	150 mg/dL - 300 mg/dL; 1.71 mmol/L - 3.42 mmol/L	>300 mg/dL - 500 mg/dL; >3.42 mmol/L - 5.7 mmol/L	>500 mg/dL - 1000 mg/dL; >5.7 mmol/L - 11.4 mmol/L	>1000 mg/dL; >11.4 mmol/L;
Leukocytosis	Total White Blood Cell Count	High			>100,000/mm ³	
White blood cell decreased	Total White Blood Cell Count	Low	<LLN - 3000/mm ³ ; <LLN - 3.0 x 10 ⁹ /L	<3000 - 2000/mm ³ ; <3.0 - 2.0 x 10 ⁹ /L	<2000 - 1000/mm ³ ; <2.0 - 1.0 x 10 ⁹ /L	<1000/mm ³ ; <1.0 x 10 ⁹ /L
Neutrophil count decreased	Absolute Neutrophil Count	Low	<LLN - 1500/mm ³ ; <LLN - 1.5 x 10 ⁹ /L	<1500 - 1000/mm ³ ; <1.5 - 1.0 x 10 ⁹ /L	<1000 - 500/mm ³ ; <1.0 - 0.5 x 10 ⁹ /L	<500/mm ³ ; <0.5 x 10 ⁹ /L
Lymphocyte count decreased	Lymphocyte Count	Low	<LLN - 800/mm ³ ; <LLN - 0.8 x 10 ⁹ /L	<800 - 500/mm ³ ; <0.8 - 0.5 x 10 ⁹ /L	<500 - 200/mm ³ ; <0.5 - 0.2 x 10 ⁹ /L	<200/mm ³ ; <0.2 x 10 ⁹ /L
Lymphocyte count increased	Lymphocyte Count	High		>4000/mm ³ - 20,000/mm ³	>20,000/mm ³	
Platelet count decreased	Platelet Count	Low	<LLN - 75,000/mm ³ ; <LLN - 75.0 x 10 ⁹ /L	<75,000 - 50,000/mm ³ ; <75.0 - 50.0 x 10 ⁹ /L	<50,000 - 25,000/mm ³ ; <50.0 - 25.0 x 10 ⁹ /L	<25,000/mm ³ ; <25.0 x 10 ⁹ /L

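### CTCAE laboratory grades are tabulated without the baseline grade, so for 19 of 25 terms an abnormality present before dosing counts as a post-dose grade

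*SAP*

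**What the plan says.** SAP 10.2 states that "grading will be applied to post-baseline values for numeric parameters where possible according to CTCAE v 5.0". Patients in each grade are counted by treatment group, term and visit. A further display takes the worst value: "Additional tables will be generated using the most severe grade after study drug administration", with unscheduled visits included. No grade is assigned to the baseline value, and nothing limits the count to grades that are new or higher than before dosing.

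The limits are in SAP Appendix 3, and they treat baseline in three ways:

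- **Relative to an abnormal baseline.** ALT Grade 1 reads ">ULN - 3.0 x ULN if baseline was normal; 1.5 - 3.0 x baseline if baseline was abnormal". Bilirubin, AST, alkaline phosphatase and GGT follow the same pattern.
- **Mixed.** Creatinine Grade 2 reads ">1.5 - 3.0 x baseline; >1.5 - 3.0 x ULN", so either limit suffices. Grade 3 is also mixed; Grades 1 and 4 use the ULN alone.
- **No reference to baseline.** Creatine kinase Grade 2 is ">2.5 x ULN - 5 x ULN", and "Lymphocyte count decreased" is graded from the LLN and fixed cut-offs.

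On shift tables, Protocol 7.8.4.3 says "Shift tables will be generated for categorical clinical laboratory test results". SAP 10.2 says "Shift tables from baseline visit to each scheduled post-baseline visit will be generated for urinalysis results", using a normal/abnormal classification, and plans none for chemistry or haematology. It does summarise change from baseline for those two groups by arm and time point.

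**The concern.** Patients enter with an acute infection, and SAP 5.2 expects 64% to be high-risk, a category that includes diabetes and chronic kidney or liver disease. No exclusion criterion sets a laboratory limit. Some graded abnormality before dosing is therefore to be expected.

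Where the limits ignore baseline, such a patient is counted after dosing even if nothing has changed. Two things follow. A true drug effect appears against a larger background and is harder to see. The rows of one table also mean different things: worsened from an abnormal baseline for the liver tests, present at any time after dosing for most other terms.

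**Working it through.** The plan states no figure that could be reproduced here. The check is a count of terms, followed by an illustration on assumed inputs.

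**Step 1: classify the Appendix 3 terms.** There are 25.

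- Fully relative to an abnormal baseline: bilirubin, ALT, AST, alkaline phosphatase, GGT (5).
- Partly: creatinine (1).
- Fixed, LLN or ULN limits only: creatine kinase; albumin; sodium high and low; potassium high and low; calcium high and low; glucose low; cholesterol; triglyceride; white cells high and low; neutrophils low; lymphocytes low and high; platelets low; haemoglobin low and high (19).

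5 + 1 + 19 = 25.

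**Step 2: follow two unchanged patients.** One has abnormal ALT at baseline and the same value afterwards. Grade 1 starts at 1.5 times baseline, so this patient is No Grade. The other has lymphopenia at baseline and the same count afterwards. This patient is graded at every visit with a sample and again in the worst-grade table.

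**Step 3: size of the dilution (illustration).** The documents supply n = 650 per arm (SAP 4.1). They give neither the baseline prevalence b, nor the risk e of a new grade among the rest on placebo, nor a drug effect. Assumed: b = 20%-40%, e = 4%-6%, and 3 points added by the drug among patients not graded at baseline. Patients graded at baseline are taken to stay graded, with no drug effect in them.

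Planned any-grade comparison: t0 = b + (1-b)e, t1 = b + (1-b)(e + 0.03), and z = (t1 - t0)/sqrt{[t0(1-t0) + t1(1-t1)]/650}.

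New grades among those at risk: z = 0.03/sqrt{[e(1-e) + (e+0.03)(0.97-e)]/[650(1-b)]}.

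For b = 0.2 and e = 0.04, t0 = 0.2 + 0.8 x 0.04 = 0.232 and t1 = 0.2 + 0.8 x 0.07 = 0.256.

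- Planned: z = 0.024/sqrt(0.36864/650) = 0.024/0.0238 = 1.01.
- New grades, 520 at risk per arm: z = 0.03/sqrt(0.1035/520) = 0.03/0.0141 = 2.13.

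| b | e | t0 v t1 | z, planned | At risk per arm | z, new grades |
|---|---|---|---|---|---|
| 0.2 | 0.04 | 23.2% v 25.6% | 1.01 | 520 | 2.13 |
| 0.3 | 0.06 | 34.2% v 36.3% | 0.79 | 455 | 1.72 |
| 0.4 | 0.06 | 43.6% v 45.4% | 0.65 | 390 | 1.59 |

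Each arm's own variance is used. Applying the smaller placebo variance to both arms would inflate the last column.

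**Step 4: the same on the ratio scale.** Take a true new-grade risk of 5% v 10%, a ratio of 2.0.

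- b = 10%: 14.5% v 19.0%, ratio 1.31.
- b = 20%: 24% v 28%, ratio 1.17.
- b = 40%: 43% v 46%, ratio 1.07.

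At b = 20%, a two-sided 5% comparison would have about 38% power on the any-grade table and about 87% among those at risk. The absolute difference shrinks only by the factor 1 - b, from 5 points to 0.8 x 5 = 4. At b = 0 the two tables coincide.

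**The case against.** Three stronger readings are tempting, and the documents do not support them.

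*Baseline is ignored throughout.* It is not. The five liver terms are graded against an abnormal baseline, and creatinine partly.

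*A drug effect would be buried.* There is a concurrent placebo arm with the same expected background. Change from baseline is summarised for every chemistry and haematology parameter, and listings carry high/low flags and grades. Clinically significant laboratory changes are recorded as adverse events (Protocol 6.2.1.1), and TEAEs are defined as new or aggravated from baseline (SAP 10.1). Each grade is tabulated separately, so severe grades have their own rows, and nothing in the documents supports a 20%-40% background for those. No test of these tables is planned. Diluted is the right word.

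*The SAP contradicts the protocol on shift tables.* Protocol 7.8.4.3 gives numeric results change from baseline and categorical results shift tables. SAP 10.2 grades numeric parameters and gives shift tables to urinalysis, so the two texts agree if only inherently categorical tests are meant. They differ only if a CTCAE grade counts as a categorical result. In that case the change belongs in SAP section 12, which does not list it. The wording is unclear rather than contradictory.

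Two practical objections stand. A baseline grade has no clear meaning for the liver terms, whose limits for an abnormal baseline are multiples of that baseline. And in Part 2 laboratory samples are scheduled at Screening (Day -7 to 1) and next at Day 2, so the baseline may be several days old.

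What the objection does not remove is the gap itself. Group summaries of change do not count patients whose grade rose. The adverse event route depends on the investigator's judgement, and Protocol 6.2.1.3 keeps worsening of the infection that is considered unrelated to study drug out of AE reporting.

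**Conclusion.** The point holds for the 19 absolute-limit terms and for the ULN-based creatinine limits. There, the visit and worst-grade tables count abnormality that was present before dosing, and a count does not mean the same thing as it does for the liver terms. The comparison between arms stays unbiased; what is lost is contrast.

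On the assumed inputs, z is about 0.65-1.0 as planned and about 1.6-2.1 for worsened grades. In two of the three scenarios the latter is still below 1.96, so the gain is in clarity and sensitivity, not in certain detection. These figures rest on assumed prevalence, incidence and effect, on baseline abnormality persisting, and on pooling all grades; the real loss could be smaller or larger.

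Severity is minor: the tables are descriptive, and the primary and key secondary analyses are unaffected.

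**What to change.** In SAP 10.2, keep the worst-grade table and add:

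1. For the 19 absolute-limit terms, and for creatinine on its ULN limits, a shift table of baseline grade (including No Grade) by worst post-dose grade, by treatment group. Baseline is as defined in SAP 5.5.
2. From that table, the number and percentage in each arm whose grade rose from baseline.
3. For bilirubin, ALT, AST, alkaline phosphatase and GGT, no change to the baseline-relative grading, with a footnote that these counts already allow for an abnormal baseline.
4. A sentence stating whether the shift tables in Protocol 7.8.4.3 are meant to cover CTCAE grades; if so, and they are not provided, an entry in SAP section 12.

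The cost is programming only, since Screening samples are already analysed centrally. There is one small downside. Because the Part 2 laboratory baseline is the Screening sample, some of the counted worsening will reflect disease course before dosing. That is expected equally in both arms and can be stated in a footnote.

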10.3. Vital Signs and Weight

Vital signs (including systolic and diastolic blood pressure, heart and respiratory rate, saturation peripheral oxygen [SpO₂] and body temperature), will be measured at each scheduled visit specified in [Appendix 1](#). Body weight will be measured at screening, prior to the study drug administration on Day 1 and on Day 90 (EOT). Height and BMI will be assessed at screening only as a baseline measurement.

Actual values and change from baseline for vital signs including weight, except for hypersensitivity monitoring results, will be summarized by treatment group at each time point using descriptive statistics. Individual vital sign measurements including body weight, except for hypersensitivity monitoring, will be presented in a data listing.

10.4. Hypersensitivity Monitoring

For hypersensitivity monitoring, additional vital signs (including systolic and diastolic blood pressure, heart and respiratory rate and body temperature) will be performed at the following time points as specified in [Appendix 1](#).

- Prior to the beginning of the study drug administration on Day 1 (within 30 minutes)

- Thirty minutes (± 15 minutes), and 60 minutes (± 15 minutes) after the start of the study drug administration
- Fifteen minutes after the end of the study drug administration (+15 minutes)
- Two hours (± 15 minutes), and 4 hours (± 15 minutes) after the start of the study drug administration

Actual values and change from baseline for hypersensitivity monitoring will be summarized by treatment group at each time point using descriptive statistics. Clinically notable hypersensitivity results of each parameter will be summarized by treatment group at each time point. The criteria for clinically notable results are defined as below.

Table 4. The Criteria for Clinically Notable Results

Parameter	Low	High
Systolic blood pressure (mmHg)	≤ 90	≥ 160
Diastolic blood pressure (mmHg)	≤ 50	≥ 90
Heart rate (beats per minute)	≤ 50	≥ 100
Respiratory rate (breaths per minute)	≤ 12	≥ 20
Body temperature ($^{\circ}\text{C}$)	≤ 35.0	≥ 38.0

Individual vital sign measurements for hypersensitivity monitoring will be presented in a data listing. High and low flags will be included in this listing to show whether a hypersensitivity result is outside of the clinically notable ranges.

